11c Strategies to improve adherence to intervention protocols, and any procedures for monitoring adherence (eg, drug tablet return, laboratory tests)

Adherence meetings are held prior to study implementation with POD-C physicians. These providers will be more likely to provide constant care in the clinic over the duration of the study as opposed to those physicians who have interim appointments. The Directors of the POD-C clinic can also request an education session at any time or new provider training if needed. Additionally, training materials will be readily accessible via all SIGHT provider prompted messaging. Strategies to improve adherence for the pediatric patients flagged by the SIGHT model is not applicable as they will follow usual care at VUMC and will not be consented and enrolled by the study team.

11d Relevant concomitant care and interventions that are permitted or prohibited during the trial

Usual pediatric care and treatments that are unrelated to genetic testing are permitted and expected to continue as normal. Interventions and treatments necessary for the immediate health and well-being of the patient, regardless of their relation to genetic testing, are anticipated as part of usual care. Any intervention by the study team that could influence the healthcare provider's decision-making process regarding genetic testing, outside of the SIGHT model's recommendations will be avoided. Interventions specifically aimed at influencing the study outcomes, such as additional prompts or incentives for genetic testing are prohibited.

Outcomes

12

Primary, secondary, and other outcomes, including the specific measurement variable (eg, systolic blood pressure), analysis metric (eg, change from baseline, final value, time to event), method of aggregation (eg, median, proportion), and time point for each outcome. Explanation of the clinical relevance of chosen efficacy and harm outcomes is strongly recommended

Primary Outcome:

Specific Measurement Variable: Number of patients

diagnosed via a Chromosomal Microarray.

Analysis Metric: Chi-square test.

Method of Aggregation: Direct case control comparison of the raw count of patients diagnosed, presented as a percentage. **Time Point:** Assessed after one year to include enough time for patients to undergo testing through usual care.

Secondary Outcomes:

Specific Measurement Variable: Duration of time to genetic testing.

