Analysis Metric: Time to event, measured from the initial patient visit to the time genetic testing is conducted.

Method of Aggregation: Median time in days

Specific Measurement Variable: Rates of genetic testing. **Analysis Metric:** Proportion of patients who received testing **Method of Aggregation:** Proportion of patients, presented as a percentage

Time Point: Assessed after one year to include enough time for patients to undergo testing through the usual course of care.

Specific Measurement Variable: Diagnosis via any genetic testing.

Analysis Metric: Proportion of patients diagnosed with a genetic disease following molecular testing or clinical evaluation. **Method of Aggregation:** Proportion of patients, presented as a percentage.

Time Point: Assessed after one year to include enough time for patients to undergo additional testing through usual care.

Specific Measurement Variable: Adherence to the SIGHT-prompted provider message.

Analysis Metric: Frequency of provider actions via referral to genetics and ordering a patient CMA following receipt of a SIGHT-prompted message.

Method of Aggregation: Proportion of instances where the provider follows the SIGHT recommendation.

Time Point: Information will be collected at the end of the study.

Participant timeline

- Time schedule of enrolment, interventions (including any run-ins and washouts), assessments, and visits for participants. A schematic diagram is highly recommended (see Figure)
 - 1. Enrollment Process: Eligibility Screening: Conducted at the initial patient visit. Consent Process: Following eligibility screening, informed consent will not be obtained as patients are following usual care.
 - **2. Interventions:** SIGHT-Prompted Provider Message: Initiated following screening for patients who meet the predefined risk threshold.
 - 3. Assessments: Baseline Assessment: Conducted during the initial visit, including collection of patient health data. Follow-up Assessments: Scheduled after initial visit to monitor the outcomes, such as number of patients receiving a diagnosis, time to genetic testing, and diagnostic yield.
 - 4. Visits: Initial Visit: SIGHT prompted provider message followed by review of referrals and documentation attributable to the initial patient visit. Subsequent Visits: Regular follow-ups as per usual pediatric care, during which recommendations and any genetic testing decisions are documented and assessed.

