 - **5. Study Close-Out:** Final Assessment: Conducted at the end of the study period to collect the final data on all outcomes.

Sample size

14 Estimated number of participants needed to achieve study objectives and how it was determined, including clinical and statistical assumptions supporting any sample size calculations

Previous data suggest that, under the usual course of care, 9% of high-risk patients (those with a predicted score of ≥ 0.3) had genetic testing. Of those, 9% received a genetic diagnosis, resulting in a genetic diagnosis rate of 0.81% (0.09*0.09) among high-risk patients

One thousand high-risk patients (score \geq 0.3) will be randomized 1:1 (500 per arm). This sample size provides 80% power to detect an increase in the genetic diagnosis rate from 0.81% under standard care to at least 3.6% with the SIGHT intervention (chi-square test, α =0.05)

Recruitment 15 Strategies for achieving adequate participant enrolment to reach target sample size

The VUMC POD-C pediatric clinic has had over 200,000 patient encounters from over the last five years with more than 30,000 unique patients and over 10,000 unique patients in 2023. The clinic averages 144 visits per day (median = 165). Estimates indicate potentially 1-2 patients flagged per day which should readily provide enough patients for an adequate sample size over a two to three-year period.

Methods: Assignment of interventions (for controlled trials)

Allocation: Sequence generation 16a

Method of generating the allocation sequence (eg, computer-generated random numbers), and list of any factors for stratification. To reduce predictability of a random sequence, details of any planned restriction (eg, blocking) should be provided in a separate document that is unavailable to those who enrol participants or assign interventions.

The SIGHT study will utilize a computer-generated assignment schedule for all patients seen in the POD-C pediatric clinic with a score greater than or equal to 0.3 for allocation into the intervention group. A computer-generated randomization schedule will be used for assigning participants to the control group. This is completed using the built-in random module of python, assigning patients with equal scores either 0 (control) or 1 (intervention) to each patient who has met all previously defined criteria, with assignments saved to a log file.

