A sample size re-estimation will be conducted after 250 patients have been randomized to account for uncertainty, and adherence rates for the initial test-referral rate used in the sample size calculation. An independent analyst, who will be blinded to the randomization assignment, will calculate the observed test-referral rate across all patients. This analysis will focus on updating the test-referral rate parameter to ensure the study is adequately powered. The updated test-referral rate will be used to reassess and, if necessary, adjust the total sample size to maintain the study's power at 80%. This process will ensure the trial remains robust and capable of detecting meaningful differences between the usual care and SIGHT-guided intervention arms.

17b If blinded, circumstances under which unblinding is permissible, and procedure for revealing a participant's allocated intervention during the trial

NA

Methods: Data collection, management, and analysis

Data collection methods

18a

Plans for assessment and collection of outcome, baseline, and other trial data, including any related processes to promote data quality (eg, duplicate measurements, training of assessors) and a description of study instruments (eg, questionnaires, laboratory tests) along with their reliability and validity, if known. Reference to where data collection forms can be found, if not in the protocol

The trial will utilize the SIGHT predictive model to generate a score for all POD-C patients. Data collection will include baseline and outcome data assessed via EHR data queries for internal genetic test orders in form of a CMA, referrals to pediatric genetics, and attributable dates. All queried metrics and additional metrics related to genetic testing results will be assessed and verified through chart review performed by a clinician (genetic counselor or geneticist) for the intervention and comparator arm for patients seen in the POD-C clinic. The validity and reliability of the SIGHT predictive model, as well as the data collection methods, have been ensured through pilot testing and chart review prior to study implementation. All data collected and related documentation will be available in the trial master file with data availability based upon institutional policy.

Plans to promote participant retention and complete followup, including list of any outcome data to be collected for participants who discontinue or deviate from intervention protocols

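### The blinded sample-size re-estimation updates a Section 14 input with an unconverted two-arm test-referral rate before one-year follow-up, so N can change even when every planning assumption is true

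*Protocol*

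**What the plan says.** Protocol Section 14 states that "under the usual course of care, 9% of high-risk patients" had genetic testing and that 9% of those tested were diagnosed. The product, 0.81%, is the control diagnosis rate. The trial is sized at 500 per arm for 80% power against 3.6%. No SIGHT-arm testing rate is given, and no time window is attached to the 9%.

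Section 17a plans a re-estimation once 250 patients are in the trial. Its stated purpose is to "account for uncertainty, and adherence rates for the initial test-referral rate used in the sample size calculation". On how the rate is obtained, the section reads: "An independent analyst, who will be blinded to the randomization assignment, will calculate the observed test-referral rate across all patients". On what is done with it, the section goes on: "This analysis will focus on updating the test-referral rate parameter". The new value then "will be used to reassess and, if necessary, adjust the total sample size", the aim being to hold power at 80%. Section 21b repeats the step at about 250 enrolled and describes it as a parameter update, not an efficacy look.

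Three other places bear on it:

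- Section 12, primary outcome: "Assessed after one year to include enough time for patients to undergo testing through usual care".
- Section 12, adherence outcome: "Frequency of provider actions via referral to genetics and ordering a patient CMA following receipt of a SIGHT-prompted message". Referral and test ordering are both counted here, whereas the Section 14 figure is patients who had testing.
- Section 15: recruitment should "provide enough patients for an adequate sample size over a two to three-year period".

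**The concern.** The re-estimation can reset the final sample size, and its stated purpose is to protect power when testing and adherence are uncertain. It names a parameter of the Section 14 calculation, and the only testing rate there belongs to usual care. The replacement is measured over both arms, so it contains the effect of the message. It is also read before the one-year window has run for anyone, and it is labelled test-referral, which is not the quantity that the 9% yield multiplies. Neither Section 17a nor Section 21b converts the pooled rate, says which effect is held fixed, or sets a follow-up condition. N would then respond to the message effect and to the speed of testing, not to an error in the planning value.

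**Working it through.** **Inputs.** From Section 14: usual-care testing 9%, yield 9%, 0.81% vs 3.6%, 80% power, 1:1, chi-square, α = 0.05 (two-sided per Section 20a). Assumed: 9% yield in both arms; SIGHT-arm testing 0.036/0.09 = 40%; the 9% read as a one-year rate.

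**Formula.** Per arm, n = [1.96·√(2p̄(1−p̄)) + 0.8416·√(p₁(1−p₁)+p₂(1−p₂))]² / (p₂−p₁)². With continuity correction, n_c = (n/4)·[1+√(1+4/(n(p₂−p₁)))]². Round up and double.

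**The plan's figure.** For 0.81% vs 3.6%, n = 433.7 (total 868) and n_c = 502.8, so 503 per arm and 1,006 in total. This reproduces the planned 1,000, and the corrected formula is used below.

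**Pooling alone, mature rate.** Pooled rate = (9% + 40%)/2 = 24.5%. Entered in place of 9%, the control diagnosis rate becomes 0.245 × 0.09 = 2.205%. The other arm depends on what is held:

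| Held | Comparison | Total N |
|---|---|---|
| Difference, 2.79 points | 2.205% vs 4.995% | 1,538 |
| 3.6% | 2.205% vs 3.6% | 4,828 |
| Ratio, 4.44 | 2.205% vs 9.8% | 356 |

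If the pooled rate is read as SIGHT-arm uptake, the comparison is 0.81% vs 2.205% and N is 2,674. The right answer is 1,006 throughout, because every planning assumption is true.

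**Lower adherence, mature rate.** Let SIGHT-arm testing be 30%. The true comparison is 0.81% vs 2.7%, which needs 1,720. The pooled rate falls to (9% + 30%)/2 = 19.5%.

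| Held | N at 40% uptake | N at 30% uptake |
|---|---|---|
| Needed | 1,006 | 1,720 |
| Difference | 1,538 | 1,368 |
| 3.6% | 4,828 | 2,614 |
| Ratio | 356 | 454 |

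With the difference or the 3.6% held, N falls when it should rise, yet both results stay above 1,000. With the ratio held, N moves the right way but from far too low a level. Exact power (chi-square with Yates correction) for 0.81% vs 2.7% is 71% at 1,368 and 53% at 1,000.

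**Timing.** 1,000 patients in two to three years is 500 to 333 a year. Patient 250 arrives at 250/500 = 0.50 to 250/333 = 0.75 year, with mean follow-up of half that, 0.25 to 0.375 year. If a share f of tests happens at the visit and the rest is spread evenly over the year, the observed rate is pooled × [f + (1−f) × mean follow-up].

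| Uptake | f | Observed rate | N: difference / 3.6% / ratio held |
|---|---|---|---|
| 40% | 0 | 6.1% | 906 / 812 / 1,490 |
| 40% | 0 | 9.2% | 1,014 / 1,022 / 986 |
| 40% | 0.5 | 16.8% | about 1,280 / 1,990 / 530 |
| 30% | 0 | 4.9% | 862 / 742 / 1,876 |
| 30% | 0 | 7.3% | 948 / 886 / 1,244 |

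At 9.2% the two distortions cancel. With uptake as planned, exact Yates power is 77% at 906 and 73% at 812, against 82% at 1,000. At 30% uptake it is 45% at 862 and 50% at 948, against 53% at 1,000. With f = 0.5 at 30% uptake, the observed rate is about 12–13% and the difference-held N is about 1,120–1,160, again above 1,000.

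**The case against.** The protocol never says in so many words that the pooled rate replaces the usual-care 9%. Section 14 does not use the term test-referral rate, and the mention of adherence in Section 17a could point to message-arm behaviour. Results from 356 to 4,828 suggest an unspecified algorithm, and the conversion, the effect held and the data cut are often left to an analysis plan, which is not at hand. Part of this stands: no single wrong N can be attributed to the protocol. But the protocol itself fixes the rate (pooled), the trigger (250), the use (reset N) and the target (a Section 14 input). The pooled rate is neither of the two quantities that it could be meant to update.

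A reader might infer that the step will leave the trial underpowered, at 45–50%. The documents do not support that. Those figures need lower uptake, an immature rate, tests spread evenly over the year, and the difference held. Even spreading fits poorly, because the message goes to the clinician for that encounter and many orders may follow at once. With a mature rate and the difference or the 3.6% held, N stays above 1,000.

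The 1,720 needed at 30% uptake powers for 2.7%, whereas Section 14 promises 80% power only from 3.6%. That is fair, but Section 17a gives uncertain adherence as a reason for the step and 80% power as its aim.

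**Conclusion.** The re-estimation rule is wrong as written and should be corrected before it is run. It enters a two-arm rate, labelled test-referral and read before one year, into a calculation whose only testing rate is a usual-care 9%. With every planning assumption true and full follow-up, it returns 1,538, 4,828, 356 or 2,674 where 1,006 is right. The pooling error needs no assumption about timing; its direction and size depend on the effect held, which the protocol does not state. Power below that of a fixed 1,000, with the difference or the 3.6% held, needs an immature rate with tests spread over the year. In some cases immaturity and pooling cancel and no material error results.

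The conclusion rests on reading the updated parameter as the 9% (or as unstated SIGHT-arm uptake), on the inferred 40%, and on a 9% yield in both arms. It is not a criticism of blinded pooled re-estimation, which is accepted practice, nor of the planned 1,000. Confidence is moderate because a separate plan could contain a conversion.

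**What to change.** Keep the analyst blinded and reword Sections 17a and 21b so that:

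1. The re-estimated quantity is the one that Section 14 uses, genetic testing, over a stated window (one year, to match the outcome), and not test-referral.
2. The calculation uses patients who have completed that window, or otherwise adjusts for follow-up.
3. The pooled rate is never entered directly as the usual-care 9% or as SIGHT-arm uptake. It is converted by a pre-stated rule that names what is held fixed. One option holds usual care at 9% and solves uptake = 2 × pooled − 9%: 24.5% returns 40% and N 1,006; 19.5% returns 30% and N 1,720.
4. 1,000 is the minimum.

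The option in item 3 must be reported with its sensitivity to the held 9%. With uptake 40%, true usual-care testing of 6% gives a pooled 23%, a solved uptake of 37% and N 1,154 where 804 is needed. True 12% gives 26%, 43% and 890 where 1,282 is needed; the minimum lifts 890 only to 1,000.

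The cost is two reworded paragraphs and a later step. If the first 250 patients must have one year of follow-up, it falls at 0.50 + 1 = 1.5 to 0.75 + 1 = 1.75 years, when 1.5 × 500 = 750 or 1.75 × 333 = about 583 are already randomized. The estimate is also imprecise: in simulation with 250 mature patients and true uptake of 40%, the N before the minimum is applied has a 95% range of about 694 to 1,696. A pooled rate of 9% or less has no useful solution under this option. Sending that case to a maximum N is a trade-off for the study team and not part of this fix.

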The allocation sequence will be generated by the study's data management team using a computer-based randomization function. Any pediatric patient scheduled for a visit in the POD-C pediatric primary care clinic at VUMC One Hundred Oaks (OHO) who meets or exceeds the predefined risk threshold will be flagged as eligible. These flagged patients will then be randomly assigned to either the intervention arm (SIGHT-prompted provider message) or the usual care arm (no provider message).

Participant Enrollment

Patients aged 1 to 20 years who have not previously undergone chromosomal microarray testing at VUMC will be automatically included in the randomization pool once they have a scheduled visit at the OHO clinic. As this study follows standard clinical care, patients themselves do not undergo a separate consent process for randomization. Instead, their providers will be informed of any SIGHT alerts only if the patient is randomized to receive them.

Assignment of Participants to Interventions

For those randomized to the intervention arm, a SIGHT-prompted provider message is generated within EPIC by a genetic counselor on the research team. This message indicates the patient's increased risk level and recommends considering a chromosomal microarray and referral to genetics. The provider maintains full discretion to act upon or dismiss this recommendation. By contrast, providers in the usual care arm receive no automated messages about SIGHT risk, and patients continue under routine care practices.

Concealment of Allocation

The randomization process is integrated into the workflow so that neither providers nor the study team can predict a patient's assignment prior to the system's automated allocation. This design ensures there is no foreknowledge of group assignment—preventing selection bias and preserving the trial's integrity.

Blinding (masking)

17a

Who will be blinded after assignment to interventions (eg, trial participants, care providers, outcome assessors, data analysts), and how

There will be no blinding of participants or physicians as patients and providers will follow usual care. Providers may dismiss the SIGHT – prompted provider message and not act on its recommendations at any time. No other intervention is planned. Patients would be unaware of the providers' decisions in that case unless the provider chooses independently to discuss the SIGHT score with them.

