The statistical analysis will utilize a chi-square test for binary outcomes such as the presence or absence of a genetic diagnosis as identified by the test or provider adherence to SIGHT message recommendations. For continuous secondary outcomes, such as the time to genetic testing, a T-test or Mann-Whitney U test will be used depending on data distribution. Subgroup analyses will involve regression methods to assess the differential effects of the intervention across subgroups defined by baseline demographic characteristics (e.g. age, sex, race). Multivariate analyses will be conducted using logistic regression for binary outcomes and linear or Cox proportional hazards regression for continuous or time-to-event outcomes, respectively. Model assumptions will be checked through the assessment of residuals and model fit will be evaluated accordingly.

When indicated, a two-sided p-value of less than 0.05 will be considered statistically significant. The Bonferroni correction will be applied to account for multiple comparisons when analyzing multiple outcomes. R will be used to perform all analyses. The analysis plan will follow the intention-to-treat principle, with all randomized participants included in the analysis according to the group to which they were allocated.

Variable/outcome	Hypothesis	Outcome measure	Methods of analysis
Primary			R will be used to perform all analysis.
Number of diagnoses via CMA	More patients are diagnosed being flagged by SIGHT via a Chromosomal Microarray	Number of patients flagged by SIGHT who receive a diagnosis via CMA over one year vs controls [binary]	Chi-square test
Secondary			
a. Time to genetic test	Patients in the intervention arm will receive genetic testing faster than those in the controlarm.	Duration in days for which patients flagged by SIGHT receive a genetic test vs control [continuous]	Cox proportional Hazards to compare the time to event (in this case genetic testing) between two groups while controlling for covariates.
b. Rates of genetic testing	Increased rates of genetic testing in the intervention arm	Rates of genetic testing ordered by providers between cases and controls over a one-year period after POD-C visit [continuous'	Binary logistic regression to calculate the odds ratio for the likelihood of receiving a genetic test in the intervention arm compared to the controls

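### Item 18a specifies no masking for the clinician who classifies CMA results, does not bar the message sender from that task, and gives no rule for what counts as a diagnosis

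*Protocol*

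**What the plan says.** Protocol item 18a (Data collection methods) obtains CMA orders, genetics referrals and dates from EHR queries. These metrics, and the additional ones on test results, are then "verified through chart review performed by a clinician (genetic counselor or geneticist) for the intervention and comparator arm". The text does not say whether the reviewer is masked to arm.

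Item 16c (Assignment of Participants to Interventions) says that the message for an intervention patient is "generated within EPIC by a genetic counselor on the research team".

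The prompt of item 17a (Blinding) asks about outcome assessors as well as participants, providers and analysts. The answer covers participants and physicians: "There will be no blinding of participants or physicians as patients and providers will follow usual care". The only role described as blinded is the independent analyst for the sample size re-estimation, who works with a pooled test-referral rate. Chart reviewers are not mentioned.

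The primary outcome (items 12 and 20a) is a binary diagnosis via CMA over one year. No criterion says which CMA result is diagnostic. Secondary outcome c is diagnosis by any test; item 12 and the registry table at the end of the protocol extend it to clinical evaluation or a clinical diagnosis by a pediatric geneticist.

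**The concern.** Providers cannot be masked in this trial, so masked outcome classification is the main protection left against detection bias. The protocol does not claim that protection. The message is generated in EPIC and the review is done from the chart, so a reviewer could probably see the arm. A reviewer who had sent the message would know it in any case.

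Without a stated rule, whether an uncertain or incidental finding makes a patient diagnosed is left to the person reading the chart. If such findings were counted more readily in the intervention arm, the comparison would shift in favour of SIGHT. The primary outcome has few events, so a small shift is not negligible.

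**Working it through.** **Inputs.** Item 14 gives the control rate, "resulting in a genetic diagnosis rate of 0.81% (0.09*0.09) among high-risk patients"; the target, "80% power to detect an increase in the genetic diagnosis rate from 0.81% under standard care to at least 3.6" per cent; the allocation, "will be randomized 1:1 (500 per arm"); and the test, "chi-square test, α =0.05". Item 20a gives the sidedness: "a two-sided p-value of less than 0.05 will be considered statistically significant".

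**Step 1: the plan's own sample size.** With p1 = 0.0081, p2 = 0.036, d = 0.0279 and mean rate p = 0.02205:

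n = [1.96·√(2p(1−p)) + 0.842·√(p1(1−p1) + p2(1−p2))]² / d² = 434 per arm.

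With continuity correction, n' = (n/4)·[1 + √(1 + 4/(n·d))]² = 503 per arm. This reproduces the stated 500 to within 1%. The protocol does not say whether the final chi-square test is corrected, so both versions are given below.

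**Step 2: expected events.** 500 × 0.0081 = 4.05 and 500 × 0.036 = 18, so about 4 against 18.

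**Step 3: robustness at the planned counts.** Control events are held at 4 and diagnoses are removed from the intervention arm. The uncorrected statistic is (difference in proportions)² / [p(1−p)·2/500], with p the pooled proportion. The corrected version first subtracts 1/500 = 0.002 from the absolute difference.

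| Counts | Uncorrected p | Corrected p |
|---|---|---|
| 4 vs 18 | 0.0025 | 0.0051 |
| 4 vs 16 | 0.0067 | 0.013 |
| 4 vs 14 | 0.017 | 0.032 |
| 4 vs 13 | 0.028 | 0.0503 |
| 4 vs 12 | 0.044 | 0.078 |
| 4 vs 11 | 0.069 | 0.119 |

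Example, 4 vs 12 uncorrected: 0.016² / (0.016 × 0.984 × 0.004) = 4.07, p = 0.044. Significance is lost at 11 events without correction (18 − 11 = 7 removals) and at 13 with correction (18 − 13 = 5 removals).

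**Step 4: how often a significant result rests on one or two intervention-arm diagnoses.** All pairs of counts were enumerated at 500 per arm and weighted by binomial probabilities at 0.81% and 3.6%. The probability summed is that the result is significant in favour of SIGHT as observed, but not after k intervention-arm diagnoses are removed.

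| k | Uncorrected | Corrected |
|---|---|---|
| 1 | 4.2% | 5.5% |
| 2 | 9.3% | 11.7% |

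**Step 5: false positives.** With 0.81% in both arms, the chance of a significant result favouring SIGHT is 2.2% (uncorrected) or 0.9% (corrected). Adding two spurious diagnoses to the intervention arm raises it to 6.5% or 3.5%.

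**Step 6: workload of masked reading.** At 9% tested, the control arm yields 500 × 0.09 = 45 reports. The protocol gives no testing rate for the intervention arm. If yield stays at 9%, a 3.6% diagnosis rate implies 0.036 / 0.09 = 40% tested, or 200 reports, for a total of 245. This is an assumption. With 20% tested the total is 145, and with 9% tested it is 90.

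**The case against.** The strongest defence is that the primary outcome is fairly objective. It requires a CMA to be ordered and a laboratory to report a result, item 20a describes the diagnosis as one identified by the test, orders and dates come from queries, and the same review applies to both arms. This stands and limits the size of the problem. It is weaker for outcome c, where clinical diagnoses count.

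A second defence is that the rule for a diagnostic result may be written in an analysis plan or review manual that is not at hand. That is possible. Whether outcome assessors are masked, however, is asked directly by the prompt of item 17a, and the answer does not cover them.

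Three stronger readings should be resisted:

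- A reader might infer that the review is declared unmasked, or that one counsellor does both jobs. The protocol states neither. It is silent on masking the reviewer and does not keep the two roles apart.
- A reader might infer that one or two reclassified results would overturn the primary test. At 4 against 18 they would not. That holds only for a result already at the boundary, as with any threshold test.
- Counting every single-patient change in either arm and either direction, 11-16% of trials lie within one change of the boundary and 23-31% within two. Those figures include non-significant results that would become significant, so they overstate the harm from a reviewer inclined towards the intervention.

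Closeness to the boundary also says nothing about how often misclassification would occur.

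**Conclusion.** The point holds as a gap in outcome assessment that can be closed cheaply. It is not an error in a stated figure and does not threaten the planned result as such. Masking the reviewers does not change the sample size.

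The exposure is modest. About 4-6% of trials at the planned rates would have a significant result resting on one intervention-arm diagnosis, and about 9-12% on two or fewer. Under no effect, two spurious diagnoses would raise the false-positive rate in favour of SIGHT about three-fold (uncorrected, 6.5/2.2) to four-fold (corrected, 3.5/0.9). These figures assume 500 per arm, the rates of item 14, a two-sided 5% level and errors only in the intervention arm. They are conditional on the number of misclassified results, and the documents give no basis for estimating that number. That the reviewer can see the arm is a probable inference, not a stated fact.

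**What to change.** In items 17a and 18a, state the following:

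1. Each CMA report is classified as diagnostic or not by a pre-specified rule, for example a laboratory-reported pathogenic or likely pathogenic finding.
2. The report is extracted without arm, message or ordering context.
3. Classification is completed before linkage to arm, by a team geneticist or counsellor who did not send that patient's message.
4. The same procedure applies to outcome c wherever a report exists.

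This needs no clinician type that item 18a does not already allow and does not alter patient care. The cost is de-identifying the reports: about 245 under the 40% testing assumption, fewer if testing is lower. Masking will remain imperfect for diagnoses made on clinical grounds alone. The registry table lists the trial as recruiting from February 2025, so the change is best made before outcomes are classified.
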